#### Safety Analysis Set (SAF)

The SAF includes all patients enrolled in the study who have received at least 1 dose of cladribine tablets (same as FAS).

#### **Additional Subgroup Analysis Populations**

	Analysis Population		
Analyses	Full Analysis Set	Per Protocol Analysis Set	Safety Analysis Set*
Baseline Assessments (baseline characteristics of patients initiating cladribine tablets, baseline PRO data, baseline laboratory data, baseline data on previous MS DMD use, relapses during the previous 2 years [or since MS diagnosis if diagnosis <24 months], baseline MRI data, retrospective MRI data	~	~	V
and past treatment adherence)			,
Compliance and Exposure	~		~
Primary Endpoint Analysis (ARR over the 24-month period)	$\checkmark$	$\checkmark$	~
Secondary Endpoints Analysis: The ARR over the 12-Month follow- up period , Sensitivity analyses of the ARR, ARR during the last 24 months (or since MS diagnosis if diagnosis <24 months) before starting cladribine tablets, Other relapse analyses	✓ 	~	×

	Analysis Population		
Analyses	Full Analysis Set	Per Protocol Analysis Set	Safety Analysis Set*
Treatment patterns (MS treatment during the last 2 years (or since MS diagnosis if diagnosis <24 months) before transition to cladribine tablets, concomitant treatment for MS, follow-up treatment in case of discontinuation of cladribine tablets)	~		~
PROs and treatment adherence	$\checkmark$		$\checkmark$
Analyses of MRI imaging data	✓		✓
JCV antibody status	✓		✓
Analyses of ALC as well as complete blood count and lymphocyte subsets, if available	✓	$\checkmark$	✓
Concomitant medications	✓		✓
Safety	✓		✓

Subgroup analyses will be performed for the primary endpoint on subgroups as defined below.

Subgroups:

The following subgroups will be defined:

- Patients completing the 24-month study
- Patients not completing the 24-month study (i.e., lost to follow-up, withdrawing consent, protocol deviations)
- Patients not completing treatment (i.e., completing Year 1 treatment but not Year 2 treatment, or not completing both courses of treatment each year)
- Type of MS at screening: RRMS, aSPMS, PPMS, CIS
- Patients diagnosed with MS <24 months before transitioning to cladribine tablets
- Centers
  - Pooling of centers: Because of the high number of participating centers and the anticipated small number of patients in each centers data will be pooled across centers, and the factor centers will not be considered in statistical models or for subgroup analyses.

## 9 General Specifications for Data Analyses

#### Data handling after cutoff date

Data after cutoff do not undergo the cleaning process. The only exceptions are the date of death and the date last known to be alive from the "End of Assessment Visit" in eCRF.

Data other than the date of death and the date last known to be alive obtained after the cutoff will not be displayed in any listings or used for summary statistics, e.g., laboratory values of samples taken after data cutoff, AEs with onset date after data cutoff, etc. will not be included in any analysis or listing.

#### Significance level

When confidence intervals (CIs) are to be calculated, these will be two-sided with a confidence probability of 95%, unless otherwise specified in this IAP. For continuous data, CIs for the mean will be calculated assuming a normal distribution of the data. CIs for binary endpoints will be presented using the Clopper-Pearson method. All statistical tests mentioned in this IAP are to be regarded as exploratory. The significance level is 5% two-sided. If p-values are to be presented for descriptive purposes it will be indicated with the statement that no inferential conclusion should be drawn from the p-value.

#### Presentation of continuous and qualitative variables

Continuous variables will be summarized using descriptive statistics, i.e.

- number of patients, number of patients with non-missing values, numbers of patients with missing values,
- mean, standard deviation (SD),
- median, 25th Percentile-75th Percentile (Q1-Q3),
- minimum, and maximum.

If there are no missing values this will be indicated by a 0.

Qualitative variables will be summarized by counts and percentages.

Unless otherwise stated the calculation of proportions will be based on the number of patients of the analysis population of interest. Therefore, counts of missing observations will be included in the denominator and presented as a separate category.

In case the analysis refers only to certain visits, percentages will be based on the number of patients still present in the study at that visit, unless otherwise specified.

#### Time to event data

Time to event data will be summarized descriptively as continuous data and using Kaplan-Meier (KM) analysis. Data summarization will include:

- Plot of KM curve with number at risk
- KM estimates with CI at fixed timepoints (e.g., every 6 months) (with number at risk/ failed)
- Median survival times with CI, and first quartile (Q1) and third quartile (Q3).

#### **Definition of Baseline**

Data entered during the baseline visit are considered baseline data for the purposes of analysis; the last value before study treatment will be considered the Baseline value. Baseline PROs can be filled out up to 7 days after the baseline visit. Baseline PRO scales will be completed before the first cladribine tablet dose is taken. Baseline MRI corresponds to the most recent MRI prior to starting cladribine tablets, which is expected to have been taken within the prior 90 days.

#### **Definition of change from Baseline**

*Change from baseline = visit value – Baseline value* 

Percent Change from Baseline = 100 \* (visit value – Baseline value) / Baseline value

#### **Definition of duration**

Duration will be calculated by the difference of stop and start date + 1 (if not otherwise specified).

The time since an event (e.g., time since first diagnosis) will be calculated as reference date minus date of event.

#### **Conversion factors**

The following conversion factors will be used to convert days into months or years:

*1* month = 30.4375 days, *1* year = 365.25 days.

#### Handling of missing data

Unless otherwise specified, missing data will not be replaced.

Missing statistics, e.g. when they cannot be calculated, should be presented as "nd". For example, if n=1, the measure of variability SD cannot be computed and should be presented as "nd".

Where tables are presented over time, the total of missing and non-missing observations at each timepoint should reflect the population still in the study at that time. For example, if a patient is still in the study at the timepoint but with missing data, it should be counted in the number of missing observations.

For PRO items with missing responses, the response will be managed as described in sections 16.3 and 16.4.

## Handling of partially missing MS onset (first attack), MS diagnosis or prior DMD medication dates

For time since MS onset, MS diagnosis or prior DMD start dates, a missing onset day/month will be replaced by 1 for the duration derivation or the derivation of DMDs used within 24 months prior to study start. For determination of whether a DMD was used within 24 months of study start, missing ending day/month of DMD use will be replaced by the end of the month, if day is missing, or December 31, if day and month are missing. If the imputed partial dates will result in an ending date for the last DMD on or after the date of first dose for cladribine then the partial dates will be re-imputed to the date corresponding to the day before the first dose of cladribine.

#### Handling of partially missing dates for relapse onset and stabilization and for first attack

To identify relapses in the past 2 years a missing day/month for the onset date will be replaced by 1, while a missing ending day/month of the stabilization will be replaced by the end of the month, if day is missing, or December 31, if day and month are missing. A missing day/month of the first attack date will be replaced by 1.

#### Time window

Day 1 is the day of the start of study dose, the day before is Day -1 (no Day 0 is defined).

Study day / Study dose day is defined relative to Day 1.

Visits will be conducted within the context of routine clinical care; thus, the timing of study visits is approximate and not mandated by the study protocol. The PDDS and the MS-TAQ will be analyzed according to the visit collected through the eCRF. For all the other PROs collected at Months 6, 12, 24, the analysis windows are  $\pm 1$  Month (30 days). The analysis windows for the different Months will be derived considering the Day 1 (day of start of study dose), regardless of possible treatment delays at the second year. Endpoints without an analysis window will be analyzed according to the visit collected through the eCRF (if available).

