9.1.1 Design Overview

This is a prospective, observational, multicenter, 30-month, Phase IV study. Sites in the US who are known to treat patients with MS will be targeted for enrollment. Patients who had decided prior to enrollment to transition from any injectable DMD to treatment with cladribine tablets under routine clinical care and who meet all eligibility criteria consistent with the approved US Prescribing Information (USPI) will receive an initial treatment course with cladribine tablets in Year 1 and are planned to receive a second course in Year 2, as per the approved USPI. Cladribine tablets are being prescribed as part of patients' standard medical care and commercial product will be used. Patients will not be provided the cladribine tablets free of charge in connection with their participation in the study. It is expected that the investigator considered the mode of action and duration of effect of the previous DMD prior to initiation of cladribine tablets. It is at the investigator's discretion to define this time period, following respective USPI. The start and end dates of each MS DMD will be recorded.

Baseline PROs, MRI and treatment adherence data will be collected before the first dose of cladribine tablets is taken. Baseline data on previous MS DMD use and relapses during the previous 2 years (or since MS diagnosis, if diagnosis <24 months) will be collected retrospectively at the Baseline Visit. All treatment decisions are at the discretion of the investigator. Patients will be followed up until the end of the observation period, irrespective if they discontinue cladribine tablets during follow-up.

During the observation period, patients will attend visits as per routine clinical practice, which are expected to happen approximately at the end of Month 2, 6 and 12 during Year 1, and at the end of Month 14, 18, and 24 during Year 2, as clinically indicated.

Post-enrollment relapse count data will be collected at Month 12 (end of Year 1) and Month 24 (end of Year 2) only. Treatment adherence data during treatment with cladribine tablets will be collected at the end of Months 1, 2, 13, and 14, while other PROs will be collected at the end of Months 6, 12 and 24.

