9.2.3 Observation Period

Each patient will be followed from the date of first dose of cladribine tablets until loss to follow-up, withdrawal of consent, death or the end of the data collection period, whichever comes first. Patients will be followed for 24 months from first dose and up to 30 months for those patients who may require a delay of initiation of Year 2 treatment for up to 6 months due to low lymphocyte counts. Follow-up will continue regardless of cladribine tablets discontinuation.

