^g Treatment adherence questions, based on modified versions of the MS-TAQ, will be completed by patients via ePRO: at Baseline Visit (modified for self-injectables to assess adherence during last previous injectable DMD treatment) as well as at the end of Month 1, Month 2, Month 13, and Month 14 (modified for cladribine tablets).

^h Baseline PRO scales will be completed before first cladribine tablet dose is taken.

ⁱ Adverse events, **C**, relapse count, and PDDS scores will be collected as per running page and will be recorded on an ongoing basis as new information is collected for up to 24 months (or 30 months if Year 2 treatment is delayed).

^j If Year 2 treatment is delayed, final follow-up visit may occur at Month 30.

Abbreviations: ALC=absolute lymphocyte count, BDI-FS=Beck-Depression Inventory-Fast Screen, CBC=complete blood count, DMD=disease-modifying drug, ePRO = electronic Patient-Reported Outcome, HIV=human immunodeficiency virus, JCV=John Cunningham Virus, MFIS-5=Modified Fatigue Impact Scale – 5-item version, MRI=magnetic resonance imaging, MS=multiple sclerosis, MS-TAQ=Multiple Sclerosis Treatment Adherence Questionnaire, PDDS=Patient Determined Disease Steps, PRO=Patient-Reported Outcome, SF36=36-Item Short Form Health Survey; TSQM=14-Item Treatment Satisfaction Questionnaire for Medication, USPI=US Prescribing Information, WPAI-MS=Work Productivity Activity Impairment – MS.

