## 5 **Objectives and Endpoints**

Objectives	Endpoints (Outcome Measures)	Endpoints (Outcome Measures) Timeframe	IAP section
Primary			
To estimate the annualized relapse rate (ARR) over a 24- month period in patients with Relapsing form of Multiple Sclerosis (RMS), including relapsing-remitting multiple sclerosis (RRMS) and active secondary progressive multiple sclerosis (aSPMS), who are treated with cladribine tablets in a real- world setting and after suboptimal response to any injectable Disease-Modifying Drug (DMD) approved in the US for RMS	ARR over 24 months of treatment with cladribine tablets (prospectively collected data)	24-month period from first dose of cladribine tablets (or 30 months if Year 2 treatment is delayed)	Section 14.1
Secondary			
To assess Patient-Reported Outcomes (PROs) and treatment adherence and treatment satisfaction during treatment with cladribine tablets	
 
Baseline scores, scores at the timepoints and change in scores from Baseline to timepoints (Month 6, 12 and 24) for the following PROs (collected via electronic PRO [ePRO] at the practice or at the patient's home): 
 
14-Item Treatment Satisfaction Questionnaire for Medication (TSQM)
 
36-Item Short Form Health Survey (SF-36)
 
Modified Fatigue Impact Scale – 5-item version (MFIS-5)
 
Beck-Depression Inventory – Fast Screen (BDI-FS) (7 items)
 
Work Productivity Activity Impairment – MS (WPAI-MS) (6 items)
 
Patient Determined Disease Steps (PDDS) scale
 
 
 
Treatment adherence based on modified versions of the MS-TAQ; data to be collected via ePRO at Baseline (modified Self-Injectables Version to assess adherence during last previous injectable DMD treatment, only baseline scores) and at the end of Months 1, 2, 13, and 14 (modified for cladribine tablets, only scores at the different time points)
 
	24-month period from enrolment Timepoints for TSQM, SF-36, MFIS-5, BDI-FS, WPAI-MS and PDDS: Baseline, months 6, 12 and 24 (or 30 months if Year 2 treatment is delayed) Adherence assessment timepoints: Baseline (adherence to previous DMD), Months 1, 2, 13, 14 (adherence to cladribine)	Section 16.3 and section 16.4

Objectives	Endpoints (Outcome Measures)	Endpoints (Outcome Measures) Timeframe	IAP section

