## 6 Overview of Planned Analyses

There will be a baseline analysis, 3 interim analyses and a final analysis. Baseline and interim analyses are descriptive and for monitoring purposes. Multiplicity corrections will not be considered. Statistical analyses will be performed using the Electronic Case Report Form (eCRF) data gained until the cutoff dates described in the following subsections.

If the start of cladribine Year 2 treatment needs to be delayed (e.g., to allow for lymphocyte recovery to at least 800 cells per microliter), all Year 2 visits and procedures will be moved out accordingly (at most 6 months). If recovery to 800 cells/mL is not complete after the 6-month delay, Year 2 treatment should not be initiated; the patient will nonetheless be followed up until the end of the observation period.

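### The Month 24 window for five PROs is fixed to Day 1, so a Year 2 delay beyond 30 to 60 days leaves the final score with no place in the Month 24 summary

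*SAP*

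**What the plan says.** SAP Section 5 gives the timepoints for TSQM, SF-36, MFIS-5, BDI-FS, WPAI-MS and PDDS as baseline and "months 6, 12 and 24 (or 30 months if Year 2 treatment is delayed". Section 6 adds that, if the start of Year 2 treatment is delayed, "all Year 2 visits and procedures will be moved out accordingly (at most 6 months". The protocol agrees: Section 9.2.3 allows for "a delay of initiation of Year 2 treatment for up to 6 months due to low lymphocyte counts", and a footnote to Table 1 in Section 9.2.4 says "If Year 2 treatment is delayed, final follow-up visit may occur at Month 30".

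Under Time window, SAP Section 9 sets windows of ±1 month (30 days) at Months 6, 12 and 24 for these PROs except PDDS, and fixes the anchor: "The analysis windows for the different Months will be derived considering the Day 1 (day of start of study dose), regardless of possible treatment delays". PDDS is treated differently: "The PDDS and the MS-TAQ will be analyzed according to the visit collected through the eCRF". Endpoints that have no window also go by eCRF visit, but these five have one. There is no Month 30 window and no rule for a final score outside the Month 24 window. Section 16.3 does not supply one either.

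Under Handling of missing data, Section 9 does not replace missing values by default, and "if a patient is still in the study at the timepoint but with missing data, it should be counted in the number of missing observations".

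**The concern.** For a patient whose second course is delayed, Sections 5 and 6 place the final PRO after Month 24, and Section 9 looks for it only around Month 24 from first dose. Beyond a short delay the two no longer meet. The score is collected as planned but has no place in the Month 24 summary of five of the six PROs, while the sixth, PDDS, is kept.

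No other scheduled assessment can fill the gap. Protocol Section 9.1.1 says of the PROs other than adherence: "while other PROs will be collected at the end of Months 6, 12 and 24". None of the five is scheduled at Month 14 or Month 18.

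Two things are at stake. First, the loss may be informative: low lymphocyte count is the main cause of delay that the documents name, alongside unspecified other clinical factors, so the patients who drop out of the Month 24 summary would not be a random subset. Second, the text leaves room for two programmers to produce different Month 24 tables.

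**Working it through.** **Inputs**
- Month length: 30.4375 days (SAP Section 9, Conversion factors).
- Window: ±30 days, anchored at first dose (SAP Section 9, Time window).
- Delay of Year 2: 0 to 6 months, shifting all Year 2 visits by the same amount (SAP Section 6).

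**The plan's own figure.** Latest final timepoint: 24 + 6 = 30 months. This reproduces the Month 30 in SAP Section 5 and in Protocol Table 1.

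**Month 24 window.** 24 × 30.4375 = 730.5 days, so the window is 730.5 ± 30 = days 700.5 to 760.5.

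**Shifted Visit 6.** For a delay of d months the visit is due on day (24 + d) × 30.4375. The excess over the window is that day minus 760.5.

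| Delay (months) | Visit 6 due (day) | Days past window | Day if 30 days early |
|---|---|---|---|
| 0 | 730.5 | inside | 700.5, inside |
| 1 | 760.9 | 0.4 | 730.9, inside |
| 2 | 791.4 | 30.9 | 761.4, outside |
| 3 | 821.8 | 61.3 | 791.8, outside |
| 6 | 913.1 | 152.6 | 883.1, outside |

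**General rule.** With a delay of D days and a visit deviation of e days (negative if early), the score is in the window only if −30 ≤ D + e ≤ 30. An on-schedule visit is therefore lost once D exceeds 30 days. A visit up to 30 days early is lost once D exceeds 60 days.

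**Can another visit supply the value?** With a 6-month delay, Visit 5 moves to (18 + 6) × 30.4375 = day 730.5, exactly Month 24 from first dose. Protocol Table 1 schedules none of the five PROs at that visit.

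**Sensitivity to the day convention**
- Half-width of 30.4375 days instead of 30: the window is 700.1 to 760.9. A 1-month delay sits on the edge, and a 2-month delay needs a visit 30.4 days early.
- 30-day months throughout: the window is 690 to 750. A 1-month delay sits on the edge (day 750), and a 2-month delay (day 780) needs a visit exactly 30 days early.
- The absence of a Day 0 shifts visit and window equally and cancels.

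Only the boundary moves. Delays of 3 to 6 months are outside by about 60 to 153 days under every convention.

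**If the window followed the delay.** Its centre would be 730.5 + 30.4375d: day 791.4 at 2 months (window 761.4 to 821.4) and day 913.1 at 6 months (window 883.1 to 943.1). An on-schedule final score would then be inside for every delay from 0 to 6 months.

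**The case against.** The strongest reply is that the anchor was chosen on purpose. The wording in Section 9 anticipates Year 2 delays, and the SAP modification history shows that version 3.0 revised these windows and removed those for PDDS and MS-TAQ. A uniform time since first dose is a legitimate target. The endpoint column of Section 5, Section 16.3 and the protocol's statistical methods all stop at Month 24, so the reference to Month 30 in the Section 5 timeframe column could be the outlier. That stands as a reason to allow the Day 1 anchor. It does not remove the conflict, because Section 5 still names a Month 30 timepoint for these PROs and Section 9 gives it no place.

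Second, the protocol says only that visits may be adjusted, and these PROs can be completed at home. A score completed near Month 24 despite the delay would fall in the window. That is possible, but SAP Section 6 says that all Year 2 procedures move, and nothing plans for a PRO at the unshifted date.

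Third, the plan never says that late scores are discarded. That is correct; exclusion follows from the window and the missing-data rule taken together. Missing counts are also tabulated by timepoint, so a shortfall would be visible, but its cause would not.

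Fourth, PDDS is not a perfect model, since a footnote to Protocol Table 1 has it recorded on a running page and does not list the other five. That stands, but mapping by eCRF visit is still the rule the SAP applies to PDDS, and Table 1 schedules all six at the same visits.

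**Conclusion.** The concern holds. SAP Sections 5, 6 and 9 conflict for any patient whose Year 2 start is delayed by more than about 30 days if the final visit is on schedule, or about 60 days if it is 30 days early. Those final scores have no place in the Month 24 summary of five PROs.

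This rests on two assumptions: that the PRO moves with the visit, as SAP Section 6 says, and that a score outside the window is not used for Month 24, which the SAP implies but does not state.

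The share of Month 24 values lost equals the share of followed patients delayed beyond those limits. The documents give no delay rate, so the number cannot be computed. The Grade 3 or higher lymphopenia frequency in Protocol Section 7.4 (about 20% to 25%) makes delay plausible but is not a delay rate. Whether the loss biases the summary is likewise possible, not shown.

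The scope is limited: one timepoint of descriptive secondary endpoints. The primary ARR and the Month 6 and Month 12 PROs are unaffected. It should be corrected before the final analysis because the data are collected and the repair is small.

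**What to change.** Reconcile SAP Sections 5, 6 and 9, and state how a final PRO outside the window is handled.

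- **Preferred:** for the final timepoint, map the five PROs by eCRF Visit 6, as is already done for PDDS.
- **Alternative:** for delayed patients who start Year 2, use a ±30-day window around 12 months after the first Year 2 dose. Use eCRF Visit 6 for followed patients who never start Year 2.
- **With either:** tabulate time since first dose at the final assessment, and show the strict Day 1 window as a sensitivity table.
- **If the Day 1 anchor is kept on purpose:** say in Section 5 that a Month 30 PRO is not part of the Month 24 summary, and report how many patients this affects.

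The cost is a short SAP edit, a change to visit mapping for five instruments and one extra set of descriptive tables; no new data are needed. The downside is wider timing. Time since first dose at the final PRO would run from about 23 months (700.5 / 30.4375) to about 31 months (943.1 / 30.4375), instead of 23 to 25, which is why the timing should be tabulated and the Day 1 window kept as a sensitivity analysis.
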